8.2.3 Efficacy

Endpoints Primary

Progression-free survival (PFS) – Progression free survival is defined as the time from the initiation of treatment to the first documented disease progression per RECIST 1.1 or death due to any cause, whichever occurs first. If a patient recurs and is eligible for retreatment, then only the time to the initial recurrence will be included in the evaluation of PFS. Patients who are alive with no evidence of disease at the time of last contact will be censored at that date.

Secondary

Overall Response Rate (ORR) – The overall response rate is defined as the percentage of the patients who have a complete response (CR) or partial response (PR) as defined by RECIST 1.1. The patient's best overall response rate defined as the best response recorded from the start of the treatment until disease progression will be recorded.

Clinical Benefit Rate (CBR) - Clinical benefit rate is the percentage of patients that have achieved a complete response, partial response, and stable disease as defined by RECIST 1.1.

Time to in-field progression – The time to in-field progression is defined as the time from initiation of treatment to progression of disease within the radiation field.

Overall Survival – Overall survival is defined as the time from first treatment until death. Patients who are alive will be censored at the last date of patient contact.

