13. A repeat biopsy may be needed to confirm disease status. See section 7.1.2.6.4 Assessment of Disease
14. Comprehensive serum chemistry panel is done as part of screening for organ function (inclusion criteria #13) is required within 21 days of start date
15. Starting with cycle 2 of pembrolizumab, CBC and CMP required prior to giving dosage can be done within 48 hours of dosage.
16. If Hep C Ab is positive a Hep C virus RNA PCR can be checked. If the Hep C virus RNA PCR is negative then the patient does not have active Hep C and therefore would still qualify for the trial.

6.2 Follow Up Phase for Patients Who Achieve a CR at Any Point During the Study or Who Complete Up to 24 Months of Pembrolizumab Without Progression of Disease.¹

Trial Period: Follow Up	Visits during the first year after the last dosage of pembrolizumab ²						Annually after 24 M visit
	3M	6M	9M	12M	18M	24M	
Visit Window	+/- 2Wk	+/- 2Wk	+/- 2Wk	+/- 2Wk	+/- 2Wk	+/- 2Wk	+/- 2 weeks
Clinical Procedures/Assessments							
Concomitant Medication Review	X	X	X	X	X	X	X
Adverse Events	X	X	X	X	X	X	X
ECOG Performance Status	X	X	X	X	X	X	X
Directed Physical Examination	X	X	X	X	X	X	X
Vital Signs and Weight ⁷	X	X	X	X	X	X	X
Efficacy Measurement							
Tumor Imaging ^{4,5}	X	X	X	X	X	X	X ⁸
Laboratory Procedures/Assessments							
Comprehensive Serum Chemistry Panel	X	X	X	X	X	X	X
CBC with Differential	X	X	X	X	X	X	X
T3, FT4 and TSH				X		X	X
Patient Reported Outcomes⁶							
EORTC QLQ C-30	X	X	X	X	X	X	X
EORTC QLQ-H&N35	X	x	X	X	X	X	X

1. Patients will undergo follow up as per this table until progression, withdrawal of consent, initiation of non-protocol anti-cancer treatment(s) or death, whichever occurs first. Definition of "first year" and "second year" are from the time of last pembrolizumab dosage. Patients who recur or progress may be eligible for retreatment discussed in section 7.1.5.2.1.

2. During the first year of follow up patients will be seen at least every 3 months. The patient can be seen more frequently if clinically indicated.

3. During the second year of follow up patients will be seen at least every 6 months. The patient can be seen more frequently if clinically indicated.

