Concomitant Medication Review	X	X	X	X	X	X	X	X	X		
Laboratory Procedures/Assessments											
CBC with Differential	X	X	X	X	X	X	X	X	X		
Comprehensive Serum Chemistry Panel	X	X	X	X	X	X	X	X	X		
Urinalysis ⁵				X			X			X ³	
T3, FT4, TSH ³				X			X			X ³	
Patient reported outcomes											
EORTC QLQ C-30	X		X		X		X		X	X ⁴	
EORTC QLQ-H&N35	X		X		X		X		X	X ⁴	
Efficacy Measurements											
Tumor Imaging ⁵			X ⁵		X ⁵		X ⁵		X ⁵	X ⁵	

1. Patients that develop a complete response during this phase of treatment will be followed as per table 6.2.
2. Patients will continue treatment with pembrolizumab for up to 24 months (from first dosage) or until progression of disease, complete response, discontinuation because of toxicity, or withdrawal from study.
3. Urinalysis and T3, FT4, TSH to be drawn before every 4th cycle (i.e. Cycle 18, Cycle 22, etc.).
4. EORTC QLQ C-30 and EORTC QLQ-H&N35 will be filled out by the patient every other cycle. The EORTC QLQ C-30 should be completed first.
5. Tumor imaging with CT neck and chest with IV contrast will be obtained after each 3rd cycle (or sooner if clinically indicated) Imaging should be reviewed to determine disease status prior to giving every 4th cycle . Definition of response is as per section 7.1.2.6.4. If the investigator feels that MRI will be the best way to follow the patient's head and neck disease subsequently, then an MRI of the neck should be done at baseline as well. However, CT scan is encouraged over MRI.
6. Vital signs to include temperature, pulse, respiratory rate, blood pressure, and oxygen saturation as measured by pulse oximeter.

6.4 Follow Up Phase for Patients with Progressive Disease or Who Discontinue Treatment Because of Toxicity or Any Other Reason (other than completing all eligible cycles of pembrolizumab treatment).

These patients will be taken off of pembrolizumab and enter the follow up phase.

Trial Phase	Safety Follow-up	Follow-up		Survival Follow-up ¹
Time from Last pembrolizumab Dose	30 days	3 months	6 months	Starting at 9 months
Visit	Safety Follow up visit	Follow up visit 1	Follow up visit 2	NA
Scheduling Window	+/- 3 days	+/- 7 days	+/- 7 days	+/- 7 days
Administrative Procedures				
Review Medications	X	X	X	
Subsequent Antineoplastic Therapy	X	X	X	X
Survival Status				X
Clinical Procedures/Assessments				
Review Adverse Events	X	X	X	
ECOG Performance Status	X	X	X	
Directed Physical Exam	X	X	X	
Vital Signs and Weight ³	X	X	X	
Laboratory Procedures/Assessments				

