CBC with Differential	X	X	X	
Comprehensive Serum Chemistry Panel	X	X	X	
Patient Reported Outcomes²				
EORTC QLQ C-30	X	X	X	
EORTC QLQ-H&N35	X	X	X	

1. During survival follow-up patients should be contacted by telephone every 12 weeks to assess for survival status until death, withdrawal of consent, or the end of the study, whichever occurs first.
2. The EORTC QLQ C-30 should be completed first.
3. Vital signs to include temperature, pulse, respiratory rate, blood pressure, and oxygen saturation as measured by pulse oximeter.

4.

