7.1.1.5.3 Subsequent Anti-Cancer Therapy Status

The investigator or qualified designee will review all new anti-neoplastic therapy initiated after the last dose of trial treatment. If a subject initiates a new anti-cancer therapy within 30 days after the last dose of trial treatment, the 30 day Safety Follow-up visit must occur before the first dose of the new therapy. Once new anti-cancer therapy has been initiated, the subject will move into survival follow-up.

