7.1.5.4 Follow-up Visits

Subjects who discontinue trial treatment for a reason other than disease progression or withdrawal of consent will move into the Follow-Up Phase and should be assessed as per Section 6.2. Every effort should be made to collect information regarding disease status until the start of new anti-neoplastic therapy, disease progression, death, end of the study or if the subject begins retreatment with pembrolizumab as detailed in Section 7.1.5.2.1. Information regarding post-study anti-neoplastic treatment will be collected if new treatment is initiated. If a new anti-neoplastic treatment is initiated during this phase, the patient will then be followed as per Section 6.4.

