7.1.5.4.1 Survival Follow-up

Once a subject experiences confirmed disease progression or starts a new anti-cancer therapy, the subject will be followed per Section 6.4. Starting at 9 months from the last pembrolizumab dose, the patient will move into the survival follow-up phase. In this phase, patients should be contacted by telephone every 12 weeks to assess for survival status until death, withdrawal of consent, or the end of the study, whichever occurs first.

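### PFS is censored at last contact although scheduled scans stop when other therapy starts, so unassessed time can count as progression-free; the size is unknown and probably small

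*Combined protocol and SAP*

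**What the plan says.** Section 8.2.3 defines PFS as time from treatment start to first documented RECIST 1.1 progression or death. Its one censoring sentence is "Patients who are alive with no evidence of disease at the time of last contact will be censored at that date". The OS definition in the same section censors at practically the same date. Section 4.2.3.1.1 defines PFS without a censoring rule. Nothing mentions the last tumor assessment or missed scans, or says how new therapy before progression is handled.

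The follow-up sections separate contact from assessment:

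- Section 6.2, footnote 1, on the chart that holds the follow-up scans: "Patients will undergo follow up as per this table until progression, withdrawal of consent, initiation of non-protocol anti-cancer treatment(s) or death".
- Section 7.1.5.4: "If a new anti-neoplastic treatment is initiated during this phase, the patient will then be followed as per Section 6.4". Section 7.1.5.4.1 agrees: "Once a subject experiences confirmed disease progression or starts a new anti-cancer therapy, the subject will be followed per Section 6.4".
- Section 7.1.1.5.3: "Once new anti-cancer therapy has been initiated, the subject will move into survival follow-up".
- Chart 6.4, as reproduced, has no imaging row. From 9 months after the last dose, its footnote 1 says "patients should be contacted by telephone every 12 weeks to assess for survival status until death".

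The title of chart 6.4 covers "Patients with Progressive Disease or Who Discontinue Treatment Because of Toxicity or Any Other Reason". Section 5.9.1, however, keeps patients who stop for reasons other than progression under disease-status follow-up, and Section 7.1.5.4 says they "will move into the Follow-Up Phase and should be assessed as per Section 6.2".

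**The concern.** Progression here is a scan-based event. After a patient moves to chart 6.4, a contact shows that the patient is alive, not that the disease is stable. If PFS is censored at that contact, the interval since the last scan enters the analysis as progression-free time. In a single-arm comparison with a fixed 8 months, no concurrent control shares the bias, and it favors the treatment.

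The sentence has a second gap. Having no evidence of disease literally describes a complete response. Patients alive with a partial response or stable disease, who may stay on pembrolizumab for up to 24 months, are not covered. Absence of documented progression was probably meant.

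Left unresolved, the censoring date for the primary endpoint would be chosen after the data are seen.

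**Working it through.** **1. The plan's own figure.** Inputs from Section 8.2.2: medians 8 and 12 months, one-sided 5%, 48 patients at 2 per month (24 months), 12 months' maturation, stated power 78%. With exponential PFS and λ = ln 2/12:

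P(event) = 1 − (e^(−12λ) − e^(−36λ))/(24λ) = 1 − (0.500 − 0.125)/1.386 = 0.7295, so 48 × 0.7295 = 35.0 events.

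Power = Φ(√35.0 × ln 1.5 − 1.645) = Φ(0.754) = 77.5%.

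The stated power reproduces, so the design arithmetic is not in question.

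**2. What is known after a patient leaves imaging.**

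| Stage | Disease assessment | Contact |
|---|---|---|
| Chart 6.2, before new therapy | Neck CT every 3 months in year 1, every 6 months in year 2 | Visits |
| Chart 6.4, to 6 months after last dose | No imaging row | Visits at 30 days, 3 and 6 months |
| Chart 6.4, from 9 months | None | Telephone, every 12 weeks |

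The 6.4 visits include a physical examination, but Section 7.1.2.6.4.2 lets only radiological measurements determine response.

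**3. Illustration of size.** The documents give no leaving rate and name no test, so these are assumptions: exponential PFS; one-sample log-rank against a median of 8, variance (O + E)/2; 15% of PFS events are deaths; scans at week 17 and then every 9 weeks; progression at its true time; median time from progression to death 2 to 3 months; 5, 10 or 20% assigned a leaving time uniform over months 1 to 6. Only those still event-free at that time leave: at 10%, 3.6 of 48. Of these, about 1 is alive at cut-off and is credited with about 19 months after the last scan (or after treatment start if there was none).

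One-sided type I error at a true median of 8 months (last-scan censoring is applied to everyone, and deaths still count):

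| Assigned to leave | Last contact, leaving unrelated to progression | Last scan, unrelated | Last contact, leaving 0–2 months before progression | Last scan, 0–2 months before |
|---|---|---|---|---|
| 0% | about 5% | 3.9% | – | – |
| 5% | 5.8–6.1% | 3.4% | 5.9–6.4% | 4.5–4.7% |
| 10% | 6.3–7.2% | 2.7–3.1% | 6.7–8.0% | 5.1–5.9% |
| 20% | 7.8–10.1% | 1.9–2.2% | 9.0–11.8% | 6.6–8.3% |

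The median estimate is 7.8 months with nobody leaving. At 10% (unrelated) it is 8.0 under last contact and 7.9–8.0 under last scan.

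If efficacy is read instead from the Kaplan-Meier estimate at 8 months, type I error is 5.5–5.7% with nobody leaving. At 10% unrelated leaving it is 7.3–7.8% under last contact and 6.2–6.5% under last scan. When leaving closely precedes progression, the two rules are practically the same on this reading.

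**4. Replacement.** Section 5.10 allows replacement of patients who withdraw before the 3-month PET/CT for reasons other than toxicity, progression or death. In the model about 63% of leavers leave before week 17. If they are replaced and excluded, last-contact type I error (unrelated leaving) is 5.0–5.2, 4.8–5.1 and 4.6–5.3% at 5, 10 and 20%, against 4.8–5.3% with nobody leaving.

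**5. A harsher variant.** With 10% of all patients actually starting new therapy before progression, a test on the log hazard, and 3 to 6 months from progression to death, last contact rejects in 6.6–10.5%, against about 4% under full observation. The median rises from 7.8 to 8.0–8.1.

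**The case against.** The strongest defense is that the sentence is conditional on there being no evidence of disease at the last contact. A survival call establishes no disease status, so the rule may never have been meant for an unscanned patient. This partly stands: what is certain is an incomplete rule, not an instruction to credit unscanned time. But the sentence does not require an assessment, and the strict reading leaves partial responders and stable patients with no rule. Either reading needs a correction.

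Second, the illustrated inflation depends on early leavers whom Section 5.10 may replace. That stands, with two caveats: leaving must count as withdrawal, and replaced patients must drop out of the analysis. Section 8.2.2 calls every entered patient evaluable and also points to the replacement rule, so this is open.

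Third, the planned summary is a median with a one-sided interval, and the median barely moves. That stands too.

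Fourth, last-scan censoring costs power, and no rule is unbiased when leaving is related to progression. True; hence the sensitivity analyses.

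A reader might infer more than the documents support:

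- That the type I figures are the expected effect. They rest on an assumed test and leaving rate, and the effect is nil if nobody leaves.
- That imaging only as clinically indicated after the 24-month visit adds to the bias. That visit is counted from the last dose, so a patient with complete response at week 17 reaches it around month 28, too late to affect an 8 to 12 month median.
- That partial responders and stable patients would be lost from the analysis, costing power. Section 8.2.2 keeps all patients in.

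**Conclusion.** The point holds as a correction to the primary endpoint's definition. As written, the censoring rule can count unassessed time as progression-free, and it does not literally cover living patients with a partial response or stable disease. The direction favors the treatment.

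The size is unknown and probably small. At 10% assigned to leave, the median shifts by about 0.2 months (up to 0.3 in the harsher variant). Type I error of about 6 to 7% is an illustration under an assumed log-rank test, and in that model it returns to about 5% if early leavers are replaced and excluded. The censoring behind the 8-month figure is not given; if it was also last contact, part of the effect would cancel. The change is still worth making before analysis because it is cheap and fixes the date in advance.

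**What to change.** Replace the PFS censoring sentence in Section 8.2.3 with:

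> Patients alive without documented progression, whatever their response, are censored at the last adequate tumor assessment, or at the start of treatment if there is none; death without documented progression is an event on the date of death.

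Keep last-contact censoring for OS. In addition:

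- Pre-specify two sensitivity analyses: the current last-contact rule, and counting new therapy or loss of imaging as an event.
- Report how many patients left imaging before progression, and why.
- If censoring at the last assessment before new therapy is also shown, label it as biased toward the treatment when leaving precedes progression. With leaving 0 to 2 months before progression, its type I error is 9.9–10.1% at 10% assigned and about 21% at 20%.
- Reconcile the title of chart 6.4 with Sections 5.9.1 and 7.1.5.4, so that it is clear which schedule applies to patients who stop without progression.

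The cost is SAP wording and two analyses on dates already collected. The statistical price, under the same assumed log-rank test at a true median of 12 months, is power of about 78% with nobody leaving (81% if status is known to cut-off), 75% at 5% assigned to leave, 71% at 10% and 63–64% at 20%. When leaving is unrelated to progression the test is conservative, with type I error of about 3% at 10%. When leaving closely precedes progression, the rule removes only part of the inflation.

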8.2.4. Biostatistical considerations in relation to proton therapy

For the primary toxicity and efficacy analyses, toxicity and efficacy outcomes will be recorded and analyzed without stratification for radiation modality. While proton has some unique

qualities compared to photon (described in section 4.2.2.2), currently, there has not been a direct prospective comparison of photon and proton radiation, and therefore it is not known whether there is any difference in efficacy, toxicity, or immunogenicity between photons and protons in reirradiation of HNSCC. Therefore, pre-specified stratification is not required. Proton is also not an experimental treatment itself and therefore it does not need to be added as an additional experimental arm in this trial.

In regards to the continuous toxicity evaluation (section 8.2.1 above) It is expected that early grade 4+ radiation toxicity will generally be observed in the high-dose region where radiation is given to gross disease. It should be noted that as described in section 4.2.2.2 above, the main difference between proton and photon is the dose to normal tissue rather than the high dose to the target volume ie high-dose region. However, in order to add extra safeguards with proton therapy, when 5 proton patients have been accrued and pass the 7 week mark on trial, the DSMB will review the data at that time and compare toxicity of proton patients to photon patients, to determine if further proton therapy should be allowed. The trial will continue to enroll photon patients during that review however proton patients will not be allowed until after the DSMB review. If the first 5 patients are enrolled before a total of 20 patients have gone past week 7, then after this review of the proton patients, the trial will continue to accrue to the 20 initial patients as described above, with subsequent DSMB review either when the toxicity threshold is crossed or when 20 total patients (includes proton and photon) have gone past the 7 week mark. If the toxicity boundary is crossed, the independent DMSB will be charged with reviewing the data including whether there is any statistical reason to believe that the incidence of grade 4+ toxicities is less or more in the proton therapy cases. If this should be the case, the DMSB may advise as to whether only photon or only proton patients should continue accrual. Similarly, when the 20 patients pass week 7 if the toxicity threshold is not met the DSMB will again evaluate toxicity for proton vs. photon patients.

If the first 5 proton patients are not accrued until after the first 20 patients, then similarly when 5 patients are accrued the DSMB will evaluate the data compared to photon to make a decision as to whether the option of proton therapy should still be allowed.

In regards to the efficacy questions, the main hypothesis is that radiation will be synergistic with pembrolizumab because of the immunogenic effect of radiation detailed prior in the protocol.

Proton radiotherapy induced cell death is the same mechanism as in photon radiation. Therefore, we would not expect a different effect on the target volume. There is a hypothetical difference in that less normal tissue exposure from proton may lead to less killing of lymphocytes and thus might be hypothetically more immunogenic than IMRT. However, this is only hypothetical, and it is unclear if this plays a significant role in the immunogenic effects of radiation in humans.

Therefore, we assume that there is no effect of radiation modality on efficacy. The primary efficacy analysis will therefore not have a pre-specified stratification for radiation modality, nor is the study powered to allow for any formal comparison between radiation modalities.

However, provided that at least 10 patients each are treated with protons and photons, in addition to analyzing the entire cohort of patients, the toxicity profile and efficacy data will be retrospectively analyzed by radiation modality.

9.0 LABELING, PACKAGING, STORAGE AND RETURN OF CLINICAL SUPPLIES

9.1 Investigational Product

The performance site principal investigator shall take responsibility for and shall take all steps to maintain appropriate records and ensure appropriate supply, storage, handling, distribution and usage of investigational product in accordance with the protocol and any applicable laws and regulations.

Pembrolizumab will be provided to the performance sites by Merck as summarized in Table 13. Sites will complete the Drug Request Form (provided as a document separate from this protocol), and send via email to [name] ([contact]) and [name] ([contact]).

Table 13. Product Description

Product Name & Potency	Dosage Form
Pembrolizumab 100 mg/ 4mL	Solution for Injection

9.2 Packaging and Labeling Information

Clinical supplies will be affixed with a drug label in accordance with regulatory requirements.

9.3 Clinical Supplies Disclosure

This trial is open-label. The subject, the trial site personnel, the Sponsor and/or designee are not blinded to treatment. Drug identity (name, strength) is included in the label text. Random code/disclosure envelopes or lists are not provided.

9.4 Storage and Handling Requirements

Clinical supplies must be stored in a secure, limited-access location under the storage conditions specified on the label.

Receipt and dispensing of trial medication must be recorded by an authorized person at the trial site.

Clinical supplies may not be used for any purpose other than that stated in the protocol.

